The abbreviated cancer-specific CGA was also found to be feasible for use by the Cancer and Aging Leukemia Group-B (CALGB 360401). Previous clinical studies, including the FOCUS2 trial, have demonstrated that factors within a CGA can better assess toxicities and aid with management decision. Based on these data, therefore, our study will incorporate CGA to assess the relative safety profile of regorafenib in the elderly population. The specific instruments used in our study have been slightly modified from the CGA data published by Hurria et al but address identical geriatric domains of interest. This CGA format is currently used in the SOCARE (Specialized Oncology Care and Research in the Elderly) multi-disciplinary clinic based at the University of Rochester Medical Center that is run by [name]. Staff at all sub-sites will be trained to conduct the CGA in a similar and replicable manner. This training will be overseen by [name] and her experienced staff.

COMPREHENSIVE GERIATRIC ASSESSMENT

DOMAIN	TOOL	SCORE SIGNIFYING IMPAIRMENT
Background Information	➤ Demographics: ➤ Education ➤ Marital status ➤ Living Arrangements ➤ Health status ➤ Employment status ➤ Driving status ➤ Age ➤ Zip code ➤ Gender ➤ Ethnicity ➤ Race ➤ Insurance/health care ➤ Income ➤ Social Services	
Physical function	➤ ADL ➤ IADL ➤ Fall history	➤ Any ADL or IADL impairment ➤ Any history of fall
Objective physical performance	➤ SPPB	➤ ≤ 9
Comorbidity	➤ Average number of comorbid conditions	➤ >5
Nutrition	➤ BMI ➤ MNA	➤ <21 ➤ ≤ 11
Social support	➤ OARS Medical Social Support	➤ Any deficit noted
Polypharmacy	➤ Number of total medications	➤ ≥5 medications
Psychological	➤ GDS	➤ ≥ 5
Cognition	➤ BOMC ➤ Mini Cog	➤ >10 ➤ abnormal
Screening	➤ VES-13	➤ ≥3
Quality of Life	➤ FACT-C ➤ FACT-F ➤ MDASI	

ADL: Activity of daily living  
MNA: Mini nutritional assessment  
SPPB: Short physical performance battery  
BMI: Body mass index  
VES: Vulnerable elderly survey  
MDASI: MD Anderson Symptom Inventory

GDS: Geriatric Depression scale  
IADL: Instrumental activity of daily living  
BOMC: Blessed orientation-memory-concentration  
FACT-C: Functional Assessment of Cancer Therapy-Colon  
FACT-F: Functional Assessment of Cancer Therapy-Fatigue

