### Secondary Objectives

- To evaluate efficacy of regorafenib in older adults with mCRC (RR, PFS, DCR and OS)
- To explore association between baseline CGA findings and risk of toxicities
- To explore the association of toxicities with CGA domain changes over time
- To assess patient-reported QOL on regorafenib over time

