## 8. Prevention/Management Strategies for Diarrhea, Hand-Foot Skin Reaction, Hypertension, and Liver Function Test Abnormalities

### Diarrhea

Diarrhea can be a common side effect of regorafenib. The preventive/management strategies for diarrhea should be consistent with local standards (e.g., anti-diarrheals and optimized hydration status).

Anti-diarrhea medications may be introduced if symptoms occur. Previous trials have shown that diarrhea can be managed with loperamide. The recommended dose of loperamide is 4 mg at first onset, followed by 2 mg every 2 to 4 hours until diarrhea-free for 12 hours.

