
3
 
Systolic BP ≥ 160 mmHg or diastolic BP ≥ 100 mmHg OR More than one drug or more intensive therapy than previously used indicated
	
Treat with the aim to achieve diastolic BP ≤ 90 mm Hg: Start anti-hypertensive medication
 
AND/OR Increase current anti-hypertensive medication
 
AND/OR Add additional anti-hypertensive medications.
	
 
• Hold regorafenib until diastolic BP ≤ 90 mm Hg, and if symptomatic, until symptoms resolve.a
 
• When regorafenib is restarted, continue at the same dose level.
 
• If BP is not controlled with the addition of new or more intensive therapy, reduce by 1 dose level.b
 
• If Grade 3 hypertension recurs despite dose reduction and antihypertensive therapy, reduce another dose level.c
 

4
 
Life-threatening consequences (eg, malignant hypertension, transient or permanent neurologic deficit, hypertensive crisis)
	Per institutional guidelines	Discontinue therapy

a. Patients requiring a delay of >4 weeks should go off protocol therapy
 
b. If BP remains controlled for at least one cycle, dose re-escalation permitted per investigator's discretion.
 
c. Patients requiring >2 dose reductions should go off protocol therapy.
		

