#### **Intensity**

The intensity of the AE is classified according to the CTCAEv4.0. Grade refers to the severity (intensity) of the AE:

**CTCAEv4 Grade 1:** mild; asymptomatic or mild symptoms; clinical or diagnostic observations only; intervention is not indicated.

**CTCAEv4 Grade 2:** moderate; minimal, local, or noninvasive intervention is indicated; limiting to age-appropriate instrumental activities of daily living (ADL; instrumental ADL refers to preparing meals, shopping for groceries or clothes, using the telephone, managing money, etc).

**CTCAEv4 Grade 3:** Severe or medically significant but not immediately life threatening; hospitalization or prolongation of hospitalization is indicated; disabling; limiting to self care ADL (self care ADL refers to bathing, dressing and undressing, feeding self, using the toilet, taking medications, and not bedridden).

**CTCAEv4 Grade 4:** life-threatening consequences; urgent intervention is indicated.

**CTCAEv4 Grade 5:** death due to an AE.

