## 12. Statistical Methods and Determination of Sample Size

### Statistical and analytical plans

The primary end-point is grade 3-5 toxicity incidence rates. Adverse events will be grouped by system organ class and graded using NCI CTCAE version 4.0. Descriptive statistics (counts and percentages) for grade 3 and 4 toxicity rates and all-grade skin toxicity will be assessed and evaluated in relation to CGA domains.

Relative dose intensity (dose reductions, dose delays, or inability to tolerate treatment) for regorafenib will be calculated. Specific toxicities associated with dose reductions, delays and/or early discontinuation of treatment course will be identified.

Efficacy outcomes will be response rate (RR), disease control rate (DCR), progression-free survival (PFS) and overall survival (OS). Best response will be classified per RECIST criteria into complete response (CR), partial response (PR), stable disease (SD) and progressive disease (PD). Disease control will be the combination of CR + PR + SD. Kaplan-Meier survival curves will be used to estimate median PFS and OS. All statistical tests will be conducted using SAS version 9.2 (SAS Institute Inc).

Analysis of CGA results will be descriptive and will describe mean, median and standard deviations of scores at baseline and at follow up time points. CGA deficits will be captured at baseline and follow up time points. Each domain will be evaluated individually and scores will be compared between baseline and follow up time points. Overall CGA deficits will be examined and proportion of patients who decline in more than 1 domain will be determined for each time point.

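### The CGA Polypharmacy count rises with study drug and with toxicity treatment, so part of the measured decline, and of its association with toxicity, is definitional

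*Combined protocol and SAP*

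**What the plan says.** Section 12 (Statistical and analytical plans) states: "Analysis of CGA results will be descriptive and will describe mean, median and standard deviations of scores at baseline and at follow up time points". Domains are then compared one by one between baseline and follow-up, and the "proportion of patients who decline in more than 1 domain will be determined for each time point". The section does not say whether decline means a worse score or crossing the impairment cut-off, nor which domains count. It also says that toxicity rates will be evaluated in relation to CGA domains. Section 2 lists a matching secondary objective: "To explore the association of toxicities with CGA domain changes over time".

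In the CGA table of Section 1, Polypharmacy is a domain with the tool "Number of total medications" and a cut-off of five or more. The Table of Assessments (footnote f) allows the baseline CGA as late as the week 1 visit, provided it precedes dispensing of regorafenib.

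Toxicity management in Section 8 adds medication. For diarrhea, "Anti-diarrhea medications may be introduced if symptoms occur". For Grade 3 hypertension, Table 8-3 includes the option "Add additional anti-hypertensive medications". For hand-foot skin reaction, emollients, urea creams, topical steroids and topical analgesics are listed.

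Section 11 (Intensity) describes Grade 3 partly as "disabling; limiting to self care ADL", while the CGA Physical function domain treats any ADL or IADL impairment as a deficit.

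**The concern.** The medication count is compared between a time when no patient can be on study drug and times when patients are on it and may be receiving drugs for its side effects. A rise can then reflect the trial's own prescribing rather than a change in geriatric status. Because the added drugs are given for toxicity, patients with toxicity will tend to show more Polypharmacy decline whether or not anything else has changed.

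Hypertension tightens the link. In Table 8-3, needing more than one drug, or more intensive treatment than before, is itself a criterion for Grade 3. The same prescription can raise the toxicity grade and the medication count.

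The study has one arm, so no concurrent group can show how much of the change is prescribing. The definitions in Section 12 are the main protection against reading it as deterioration.

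**Working it through.** The plan states no expected CGA decline rate, so there is no figure to reproduce. The check has two parts: what the rules do to individual patients, and how far that can carry into the composite.

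**1. Individual patients (cut-off five or more, from the CGA table)**
- On 4 drugs at baseline: 4 + regorafenib = 5. Crosses regardless of toxicity.
- On 3 drugs: 3 + regorafenib + one toxicity drug = 5. Crosses because of toxicity.
- On 5 or more: already impaired, so cannot cross.
- Already on an antihypertensive and develops Grade 2 hypertension: Table 8-3 calls for a higher dose, so the count need not change.

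Whether topical products count, and whether regorafenib is entered at a CGA falling in the week off treatment, is not stated.

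**2. Contribution to the composite**

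Polypharmacy is one domain, so a second must also decline. Suppose six other domains (the number named in Section 4) each decline independently with probability q, unrelated to toxicity. Let c be the probability that Polypharmacy declines. Then

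P(at least 2 domains) = (1 − c) × P(at least 2 of 6) + c × P(at least 1 of 6),

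and the increase due to Polypharmacy is c × P(exactly 1 of 6) = c × 6q(1 − q)^5.

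| q (assumed) | Without Polypharmacy | If Polypharmacy always declines | Difference |
|---|---|---|---|
| 5% | 3.3% | 26.5% | 23.2 points |
| 10% | 11.4% | 46.9% | 35.4 points |
| 20% | 34.5% | 73.8% | 39.3 points |

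For c, assume a Poisson baseline count with mean 3, 5 or 7:

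| Mean | Already at 5 or more | On exactly 4 | On 3 or 4 |
|---|---|---|---|
| 3 | 18.5% | 16.8% | 39.2% |
| 5 | 56.0% | 17.5% | 31.6% |
| 7 | 82.7% | 9.1% | 14.3% |

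*Decline means crossing the cut-off.*
- One added drug, which may be regorafenib alone: c runs from 9.1% to 17.5%. The increase runs from 0.091 × 0.232 = 2.1 points to 0.175 × 0.393 = 6.9 points.
- Two added drugs, for example regorafenib and one toxicity drug: c runs from 14.3% to 39.2%. The increase runs from 0.143 × 0.232 = 3.3 points to 0.392 × 0.393 = 15.4 points.
- If regorafenib is left out and toxicity adds one or two drugs, the gap between patients with and without drug-treated toxicity is 2 to 15 points.

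*Decline means any increase in the count.* Here c = 1 for anyone given a further drug. If regorafenib is not counted, the gap between patients with and without drug-treated toxicity is 23 to 39 points. If regorafenib is counted, everyone's count rises (unless another drug is stopped). The same 23 to 39 points then fall on all patients, and this domain no longer separates the toxicity groups.

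The values of q, the independence and the Poisson counts are assumptions. None comes from the documents.

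**The case against.** The strongest reply is that the effect is narrow and the analysis is only descriptive. Much of this stands.

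- A reader might infer that toxicity treatment alone produces decline in more than one domain. It does not: an added drug moves one domain. Nor does Section 12 itself cross the composite with toxicity; the link arises through the domain-level evaluation and the secondary objective.
- Section 4 names function, comorbidity, nutrition, mood, social support and cognition as the domains watched for deterioration, without medications. That weakens the case but does not settle it. Section 1 includes medication review among the domains and gives it a row and a cut-off, and Section 12 excludes nothing.
- Section 12 also gives scores and deficits for each domain, so a shift confined to Polypharmacy would be visible.
- A reader might treat ADL loss as an artefact too. It is not: a patient who cannot dress because of a skin reaction has lost function. Only the strength of its association with grade is partly built in, because the grade definitions use the same concept.
- A reader might add that "Any history of fall" can only accumulate. The look-back window is not visible, since the Appendix C tools are not shown. Accumulation would not by itself tie decline to toxicity either.
- Added medication is a real burden in an older adult, which is why the full count should still be shown.

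**Conclusion.** The point holds in a limited form. Study drug and toxicity treatment inflate the Polypharmacy result, contribute one domain to the composite, and make any toxicity/Polypharmacy association partly definitional. Nothing in Section 12 removes this.

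The size cannot be computed from the documents. The illustration gives about 2 to 15 points on the composite if decline means crossing the cut-off, and 23 to 39 if any increase counts. It depends on the undefined meaning of decline, on whether Polypharmacy and regorafenib are counted, and on baseline medication use. On the cut-off reading the effect shrinks as more patients start at five or more drugs.

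A reader might go further and expect a false finding of geriatric harm, or an effect on the main result. The documents do not support that: the CGA analysis carries no test or decision rule, and the primary toxicity endpoint is unaffected. This is a low-priority improvement to a secondary, descriptive analysis.

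**What to change.** In Section 12:

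1. For CGA change, count medications excluding regorafenib at every time point. Show the count with and without drugs started to prevent or treat an adverse event, and state whether topical products count. Section 10 (Prior and concomitant therapy) already requires start and stop dates and the indication for each medication.
2. State the rule for decline. Report the proportion declining in more than one domain with and without Polypharmacy, beside the proportion improving in more than one domain by the same rule.
3. For the toxicity association, add a sensitivity result that leaves out Polypharmacy and ADL/IADL. State that ADL loss from toxicity is real but overlaps with the CTCAE grade definitions.

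Restricting the toxicity side to laboratory and blood pressure events would not serve as a substitute for item 3. Grade 3 hypertension is partly defined by drug use, so that pairing would keep the circularity if Polypharmacy stayed in.

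The cost is some wording and a few extra tables from data already collected. The reduced composite will be slightly less comparable with other CGA reports, so the full version should be kept alongside it.

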### **Determination of sample size**

Based on data from the CORRECT trial, an anticipated grade 3-4 toxicity rate of 40-50% is expected for our study. This is slightly lower than the observed grade 3-4 toxicity rate seen among patients > 65 years in the CORRECT trial. However, we hypothesize that starting at a lower dose and instituting extensive supportive care will lower the observed toxicity rate in our patient population. Using a sample size of 60 subjects with an expected toxicity rate of 45%, we will have a 90% CI of [0.341, 0.564] and an approximate 12% margin of error. Our plan is to accrue 3-4 patients per month among the four participating sites.

### **13. Premature Termination of the Study**

- If risk-benefit ratio becomes unacceptable owing to, for example,
  - Safety findings from this study (e.g. SAEs)
  - Results of parallel clinical studies
  - Results of parallel animal studies  
(on e.g. toxicity, teratogenicity, carcinogenicity or reproduction toxicity).
- If the study conduct (e.g. recruitment rate; drop-out rate; data quality; protocol compliance) does not suggest a proper completion of the trial within a reasonable time frame.

The investigator has the right to close his/her center at any time.

For any of the above closures, the following applies:

- Closures should occur only after consultation between involved parties (Coordinating Center and enrolling site).
- All affected institutions (e.g. IEC(s)/IRB(s); competent authority(ies); study center; head of study center) must be informed as applicable according to local law.
- In case of a partial study closure, ongoing subjects, including those in post study follow-up, must be taken care of in an ethical manner.

Details for individual subject's withdrawal can be found in Section 6.

## 14. Ethical and Legal Aspects

### Ethical and legal conduct of the study

The procedures set out in this protocol, pertaining to the conduct, evaluation, and documentation of this study, are designed to ensure that the investigator abide by Good Clinical Practice (GCP) guidelines and under the guiding principles detailed in the Declaration of Helsinki. The study will also be carried out in keeping with applicable local law(s) and regulation(s).

#### Investigator Requirements:

Strict adherence to all specifications laid down in this protocol is required for all aspects of study conduct; **the investigator may not modify or alter the procedures described in this protocol.**

Modifications to the study protocol will not be implemented by the investigator without discussion and agreement by the Coordinating Center. However, the investigator may implement a deviation from, or a change of, the protocol to eliminate an immediate hazard(s) to the trial subjects without prior IEC/IRB/Coordinating Center approval/favorable opinion. As soon as possible, the implemented deviation or change, the reasons for it and if appropriate the proposed protocol amendment should be submitted to the IEC/IRB/head of medical institution. Any deviations from the protocol must be explained and documented by the investigator and reported to the Coordinating Center by faxing: [contact].

The Principal Investigator is responsible for the conduct of the clinical trial at the site in accordance with Title 21 of the Code of Federal Regulations and/or the Declaration of Helsinki. The Principal Investigator is responsible for personally overseeing the treatment of all study patients. The Principal Investigator must assure that all study site personnel, including sub-investigators and other study staff members, adhere to the study protocol and all applicable FDA/GCP/NCI regulations and guidelines regarding clinical trials both during and after study completion.

The Principal Investigator at each institution or site will be responsible for assuring that all the required data will be collected and properly documented.

### 15. Publication policy

The Coordinating Center recognizes the right of the investigator to publish results upon completion of the study. However, the investigator must send a draft manuscript of the publication or abstract to the Coordinating Center (who will then forward this to Bayer) at least

thirty days in advance of submission in order to obtain approval prior to submission of the final version for publication or congress presentation. This will be reviewed promptly and approval will not be withheld unreasonably. In case of a difference of opinion between the Coordinating Center (including Bayer) and the investigator(s), the contents of the publication will be discussed in order to find a solution which satisfies both parties. All relevant aspects regarding data reporting and publication will be part of the contract between the Coordinating Center and the investigator/institution.

The Principal Investigator should ensure that the information regarding the study be publicly available on the internet at [www.clinicaltrials.gov](http://www.clinicaltrials.gov).

## **16. Confidentiality**

All records identifying the subject will be kept confidential and, to the extent permitted by the applicable laws and/or regulations, will not be made publicly available.

Should direct access to medical records require a waiver or authorization separate from the subject's statement of informed consent, it is the responsibility of the Investigator to obtain such permission in writing from the appropriate individual.

## 18. Appendices

### Appendix A – RECIST 1.1 Criteria

	RECIST 1.1
Measurable Disease: Tumor Lesions	
Tumor lesions must be accurately measured in at least one dimension (longest diameter in the plane of measurement is to be recorded with a minimum size of):
 
 
- 10mm by CT /MRI scan (scan slice thickness no greater than 5mm)
 
- 10mm caliper measurement by clinical exam (lesions which cannot be accurately measured with calipers should be recorded as non-measurable)
 
- 20mm by chest X-ray
 

Measurable Disease: Malignant Lymph Node	
Sum of the diameters (longest for non-nodal lesions, short axis for nodal lesions)
 
Measure SHORT axis:
 
 
- Target lesion if short axis <math>\geq 1.5</math>cm
 
- Non-target if short axis 1.0 to <math><1.5</math>cm or pathological
 
- Normal lymph node if short axis <math>< 1.0</math>cm
 
 
Add ACTUAL short axis measurement to sum of longest diameters of non-nodal lesions.

Target Lesions	
All measurable lesions:
 
 
- Up to 5 target lesions max in total
 
- Up to 2 target lesions max per organ
 

Non-Target Lesions	
All other lesions (site of disease). Measurements are not required and these lesions should be followed as:
 
 
- Present
 
- Absent
 
- Unequivocal progression
 

New Lesions	
The appearance of new malignant lesions denotes disease progression.

Methods for Evaluation of Measurable Disease	
All measurements should be taken and recorded in metric notation, using a ruler, calipers, or digital measurement tool. All baseline evaluations should be performed as closely as possible to the beginning of treatment and never more than 4 weeks before the beginning of the treatment. The same method of assessment and the same technique should be used to characterize each identified and reported lesion at baseline and during follow-up. Imaging-based evaluation should always be done rather than clinical examination unless the lesion(s) being followed cannot be imaged but are assessable by clinical exam.

## Appendix B: Investigators Brochure

Will be provided upon request

## Appendix C: Comprehensive Geriatric Assessment Tools

CGA Team  
Assessment 12Apr20.

CGA Patient  
Assessment 12Apr20.

## Appendix D: Handout on ‘Tips for Skin Care’ for patients

STIVARGA® for  
Patients \_ Managing H

